4.2. Patient Disposition

The reasons for discontinuation from the study and discontinuation of the study treatment will be summarized for the Randomized Population by treatment group and compared between the treatment groups using Fisher's exact test. Similar summary without treatment comparison will be provided for the discontinuation reasons prior to randomization.

A listing of the primary reason for patient discontinuation from the study or patient discontinuation of the treatment medication will be generated for the All Randomized Population.

A listing of the randomization codes for this study will be provided.

4.3. Patient Characteristics

Demographic and baseline characteristics including but not limited to age (years), age groups (<65 years, ≥65 years and <75 years, ≥75 years), sex, ethnicity, race, country, region, weight (kg), body mass index (BMI: kg/m²), BMI groups (<25, ≥25 and <30, ≥30 and <35, and ≥35 kg/m²), eGFR groups (estimated glomerular filtration rate based on the modified Modification of

Diet in Renal Disease [MDRD] equation: ≥ 90 , < 90 and ≥ 60 , < 60 and ≥ 30 , and < 30 mL/min/1.73 m²), duration of diabetes (years), baseline substance use (alcohol, drug, tobacco and caffeine baseline use status), baseline systolic blood pressure, baseline diastolic blood pressure, baseline HbA1c (% and mmol/mol), baseline HbA1c groups ($< 7\%$, $\geq 7\%$ and $< 8.5\%$, $\geq 8.5\%$), fasting serum glucose (FSG: mmol/L and mg/dL), lipid measures (triglycerides, FFA, total cholesterol, HDL-C, and LDL-C), liver enzymes (ALT, AST and total bilirubin), HbA1c strata (HbA1c $< 8.5\%$ and $\geq 8.5\%$ at Visit 1), and sulfonylureas [SU] use will be summarized by treatment group using the All Randomized Population. Continuous measures will be summarized using descriptive statistics and treatment difference will be analyzed using the analysis of variance. Categorical measures will be summarized using sample size, frequency, and percentage and treatment difference will be analyzed using Chi-squared test. The by-patient listing of demographic and selected baseline characteristics will be provided for all randomized patients.

Number of randomized patients and number of patients discontinued per investigator within country for each treatment group will be summarized. In addition, number of enrolled patients per investigator within each country will also be summarized.

4.4. Concomitant Medications

Concomitant medications will be summarized by treatment group and will be compared between treatment groups using Fisher's exact test for all randomized patients. The percentages of patients who took concomitant medication will be summarized by treatment using Preferred Terms (PTs) nested within Anatomical Therapeutic Chemical (ATC) Level 3 codes. The concomitant medications will be ordered by decreasing frequency within each ATC level.

Listing of concomitant medications will be provided.

4.5. Treatment Compliance

Treatment compliance will be summarized using the EAS. For a given study participant, overall compliance for treatment period is based on the ratio of the total number of doses taken to the total number of required doses. If the ratio is less than 80%, the participant will be considered as treatment non-compliant. The compliance difference between treatment groups will be evaluated using Fisher's exact test.

Adherence to the dosing algorithm is required from Visit 3 (Randomization) up to Visit 21. The number and percentage of investigator-calculated doses that are not equal to patient actual dose will be provided.

4.6. Protocol Deviations

Important protocol deviations (IPDs) defined as deviations from the study protocol that may compromise the data integrity and patients' safety will be summarized by treatment group for all randomized patients. The listing of IPDs for all randomized patients will also be provided.

The list of pre-defined important protocol deviation was provided in the trial issue management plan. The decision and rationale for not reporting certain protocol deviations as important in the CSR will be documented in the study decisions log.

4.7. Primary Outcome and Methodology

The primary efficacy measure of change in HbA1c at Week 32 (together with HbA1c measure at other postbaseline visits) will be summarized and analyzed using an MMRM approach on the EAS. This model implicitly adjusts for missing data through a variance-covariance structure. This model will include the fixed effects of treatment (LY3209590 Algorithm 1, LY3209590 Algorithm 2, insulin degludec), stratification factors (country, BMI strata [BMI <30 or ≥30], sulfonylureas use[Y/N]), visit, treatment by visit interaction, and baseline value of the dependent variable as the fixed effects. The HbA1c is reported in unit of % and will be converted to the unit of mmol/mol using the following formula: HbA1c in mmol/mol = 10.93*HbA1c in % - 23.5 (<http://www.ngsp.org/ifccngsp.asp>). HbA1c analysis will be conducted based on both units.

In the MMRM model, the within-patient errors are modeled as an unstructured variance-covariance matrix. If the analysis fails to converge, the following variance-covariance matrix will be used (in order) until one converges:

1. toeplitz with heterogeneity
2. autoregressive with heterogeneity
3. compound symmetry with heterogeneous variances
4. toeplitz
5. autoregressive
6. compound symmetry without heterogeneous variances

The Kenward-Roger approximation will be used to estimate denominator degrees of freedom for the MMRM models. The following is an example SAS code:

```
proc mixed data=DATA;
  class TREATMENT STRATIFICATIONS VISIT PATIENT;
  model HbA1c=BASELINE TREATMENT STRATIFICATIONS VISIT
        VISIT*TREATMENT / solution ddfm=kr;
  repeated VISIT / subject=PATIENT type=un;
  lsmeans TREATMENT*VISIT/ pdiff cl alpha=0.1 om=DATA;
run;
```

The 2-sided 90% CI for the LS mean for the individual treatment arms, treatment LS mean difference (LY3209590 Algorithm 1 vs. insulin degludec, LY3209590 Algorithm 2 vs insulin degludec, and LY3209590 Algorithm 1 vs LY3209590 Algorithm 2) in the change in HbA1c at 32 weeks will be constructed. Similar summary will be provided for the comparison between pooled LY arm and insulin degludec based on the contrast from the above MMRM model.

4.8. Secondary and Additional Efficacy Analyses

The analysis population for the secondary analysis on HbA1c reduction is the EAS. Treatment comparison at 32 weeks will be used to assess the difference between the pooled LY arm and Degludec arm. The 2-sided 90% CI for the LS mean of the difference between pooled LY arm and Degludec arm in the change in HbA1c at 32 weeks will also be constructed.

A sensitivity analysis will be conducted to evaluate the “treatment policy” estimand, which is defined as the treatment differences in HbA1c at 32 weeks with the randomized treatment based

on all randomized patients who took at least one dose of study medication, and have baseline and at least one postbaseline measurement. In this analysis, all endpoint data regardless of treatment disposition status will be included and missing data will be imputed using multiple imputations to assess sensitivity to departures from the missing at random assumption. More specifically, the missing endpoint will be imputed multiple (for example, 100) times using the baseline data. Then, the inference based on the multiple imputations framework will be used (Rubin 1987).

The following secondary and additional efficacy analyses will be performed based on the EAS using the same MMRM model as the primary analysis with the addition term of HbA1c strata (<8.5% and \geq 8.5%) for non-HbA1c measures:

1. HbA1c change from baseline to Week 12;
2. Fasting blood glucose (FBG) by SMBG and change from baseline at Weeks 12 and 32;
3. Fasting serum glucose (FSG) by laboratory and change from baseline at Weeks 6, 12, 18, and 32;
4. Between-day glucose variability measured by the SD of the FBG (SMBG) at Week 12 and 32;
5. Six-point SMBG profile (pre-meal and 2-hour postprandial SMBG measurements for the morning, midday, and evening meals in 1 day) at Weeks 12 and 32. Since the baseline SMBG profile is not collected, the baseline FBG instead of baseline value of the dependent variable will be used as a covariate.
6. Within-day and between-day glucose variability measured by the standard deviation (SD) of 6-point SMBG. Since the baseline SMBG profile is not collected, the baseline SD of FBG instead of baseline value of the dependent variable will be adjusted as a covariate.

The proportion of the patients with HbA1c <7.0% (or \leq 6.5%) will be analyzed using a longitudinal logistic regression. In the longitudinal logistic regression model, the independent variables of treatment, country, BMI strata (BMI <30 or \geq 30), baseline SU use (yes or no), baseline HbA1c value, visit, and treatment by visit interaction will be used.

The insulin dose units are different between LY3209590 (mg) and insulin degudec (unit). Therefore, descriptive statistics will be provided for the insulin dose and the dose change from baseline. No treatment comparison will be conducted.

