### **Study Period 3: End-of-Treatment and Safety Follow-Up, Visits 21, 801, 802, and 803**

All randomized study participants should have a comprehensive efficacy and safety evaluation approximately 1 week after the last dose of IP and a safety follow-up visit approximately 6 weeks after the last dose of IP. During the safety follow-up study period, study participants will continue CGM and may be treated with an appropriate glucose-lowering regimen (see [Table BDCM.4](#)) if necessary. Study participants will also be required to return any remaining study diaries and used or unused IP to the investigative site.

Study participants who *complete the treatment period* will have a comprehensive End-of-Treatment efficacy and safety assessment (Week 32; Visit 21) approximately 1 week

after the last dose of IP and a safety follow-up assessment (Visit 801) approximately 6 weeks after the last dose of IP and 5 weeks after their End-of-Treatment assessment (Visit 801). During the safety follow-up study period, study participants will continue CGM, and may be treated with an appropriate glucose-lowering regimen (see [Table BDCM.4](#)) if necessary. Study participants will also be required to return any remaining study diaries and used or unused IP to the investigative site.

Study participants who *discontinue IP prior to completion* of the study for any reason should also have a comprehensive End-of-Treatment efficacy and safety assessment (Visit 802) approximately 1 week after the last dose of IP or as soon as reasonably possible thereafter, and should have a safety follow-up assessment (Visit 803) approximately 6 weeks after the last dose of IP. Study activities at Visits 802 and 803 are identical to Week 32 (Visit 21) and Visit 801, respectively.

Study participants who discontinue IP prior to study completion will be encouraged to remain in the study and to complete any scheduled study procedures that occur after their safety follow-up (Visit 803). Study participants remaining in the study will receive an appropriate rescue glucose-lowering regimen. [Table BDCM.4](#) provides details on the use of glucose-lowering medications for rescue and for treatment of acute conditions.

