### 10.2. Analysis Sets

For purposes of analysis, the following populations and analysis sets are defined:

Population and Analysis Set	Description
Enrolled	All study participants who sign informed consent
All randomized study participants	All study participants who are randomly assigned a treatment arm
Efficacy analysis set (EAS)	Data for all randomized study participants who received at least one dose of study medication, excluding data after using rescue medication or stopping study medication (last dose date + xx days). In the event of a treatment error, participants will be analyzed according to the treatment they actually received.
Full analysis set (FAS)	Data for all randomized study participants, regardless of titration, stop of study medication, or rescue.

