#### **10.3.3.2. Secondary Analyses**

The secondary analysis will be performed on the efficacy analysis set. The main secondary efficacy analysis aims to compare LY versus Insulin Degludec with regarding to HbA1c change from baseline at Week 12 and 32. The estimand of interest is the treatment differences in HbA1c at 12 and 32 weeks while the study participants are on study treatment. The efficacy analysis set (EAS) will be used to calculate the mean difference between treatments. Similar MMRM model will be used for the main secondary analysis. The least-squares (LS) mean differences and the standard errors from each imputed sample will be calculated based on the above model, and the final estimation for the means, standard errors, 90% confidence intervals, and p-values will be reported.

A supplementary analysis will be conducted to evaluate the “treatment policy” estimand, which is defined as the treatment differences in HbA1c at 32 weeks with the randomized treatment based on FAS. The estimator is defined as the mean difference between treatments based on FAS. The missing values will be imputed using multiple imputations. The similar MMRM model will be performed on imputed data and inferences will be drawn based on the framework of multiple imputations (Rubin, 1987).

In addition to the main secondary efficacy analysis of HbA1c, the following secondary efficacy outcomes will be analyzed:

- Body weight and change from baseline to 12 and 32 weeks
- Fasting blood glucose and change from baseline at 12 and 32 weeks

The analyses of the HbA1c change, mean weight change, fasting blood glucose change and SMBG change from baseline will be conducted through MMRM similar to that of the primary efficacy outcome. The corresponding baseline will be used in the model instead of the baseline HbA1c levels. The MMRM model will also include a term for the HbA1c stratification group. The treatment p-value will be used as evidence of difference between LY3209590 and insulin degludec, while the comparison of LS means versus insulin degludec (unadjusted for multiple comparisons) and its 90% confidence interval will provide magnitude and significance of this difference.

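### The SAP's treatment-policy analysis requires a dose and a postbaseline HbA1c, so it does not cover the all-randomised set on which the protocol defines that estimand

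*SAP*

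**What the plan says.** Protocol 10.3.3.2 plans a supplementary analysis for the treatment-policy estimand, "which is defined as the treatment differences in HbA1c at 32 weeks with the randomized treatment based on FAS". Protocol 10.2 defines the full analysis set (FAS) as "Data for all randomized study participants, regardless of titration, stop of study medication, or rescue". It sets no condition on dosing or on having been measured after baseline. For gaps in the data the protocol states: "The missing values will be imputed using multiple imputations".

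SAP 4.8 calls the corresponding analysis a sensitivity analysis and keeps the estimand's name, but bases it "on all randomized patients who took at least one dose of study medication, and have baseline and at least one postbaseline measurement". Within that set, "all endpoint data regardless of treatment disposition status will be included". For those without a Week 32 value, "the missing endpoint will be imputed multiple (for example, 100) times using the baseline data". The stated aim of the imputation is "to assess sensitivity to departures from the missing at random assumption".

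SAP 4.1 lists no FAS. Section 4.8 gives no reason for the narrower set, and the SAP's list of main changes does not mention it.

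Protocol 5.1.1 provides exit assessments for those who stop treatment early: "Study activities at Visits 802 and 803 are identical to Week 32 (Visit 21) and Visit 801, respectively". Participants unwilling to return for safety follow-up are asked to attend an early termination (ET) visit.

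**The concern.** One estimand name covers two populations. A treatment-policy effect compares the arms as randomised. Receiving a dose and providing a postbaseline HbA1c are both events after randomisation. In an open-label trial where one product starts with a loading dose and the other does not, either event could differ by arm for reasons related to outcome.

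This matters because no other planned efficacy analysis is meant to follow assignment. The primary and main secondary HbA1c comparisons use the efficacy analysis set, which discards data after rescue or stopping. Their repeated-measures model of change from baseline also gains no outcome information from a participant with no postbaseline value. The treatment-policy analysis is where that gap could be closed. As written in the SAP, it has the same gap.

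**Working it through.** **1. The plan's own figures.** Protocol 10.1 gives 300 completers (200 LY3209590, 100 degludec), 20% dropout, SD 1.1, margin 0.4, true difference 0 and two-sided alpha 0.10.

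- Randomised: 300 / (1 − 0.20) = 375, as stated.
- Standard error: 1.1 × √(1/200 + 1/100) = 0.135.
- Power: Φ(0.4/0.135 − 1.645) = 0.907, or 0.906 from the noncentral t with 298 degrees of freedom, against 90% stated.

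The design reproduces. These figures neither support nor refute the point; they only supply inputs for its size.

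**2. The two sets compared.**

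| Participant | Protocol FAS | SAP 4.8 set |
|---|---|---|
| Randomised, never dosed | in | out |
| Dosed, left before Week 6, no HbA1c at Visit 802 or ET | in | out |
| Dosed, left before Week 6, HbA1c at Visit 802 or ET | in | in |
| Some postbaseline HbA1c, none at Week 32 | in, imputed | in, imputed |
| Rescued or stopped treatment, Week 32 HbA1c present | in | in |

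The first postbaseline HbA1c in the Schedule of Activities is at Visit 9 (Week 6). The SAP's further requirement of a baseline value should exclude almost no one, because a screening HbA1c is an entry criterion.

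**3. How many.** The documents do not say. Assuming the planned dropout falls evenly over 32 weeks, those leaving before Week 6 number 375 × 0.20 × 6/32 = 14.1. A constant hazard reaching 20% at Week 32 gives 375 × (1 − 0.8^(6/32)) = 15.4. Both count leavers before any deduction for HbA1c taken at Visit 802 or ET. Front-loaded dropout would raise them. If the excluded share is anywhere from 0% to 10%, then 0 to about 38 participants are dropped.

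**4. How much the estimate could move.** Let e be the share excluded in an arm and g the amount by which the excluded participants' Week 32 HbA1c exceeds that of those kept. The LY minus degludec difference on all randomised participants exceeds the restricted difference by

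e_LY × g_LY − e_D × g_D.

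- Equal e and equal g in both arms: 0.
- Assumed 6% LY and 2% degludec, common g of 0.5 to 1.0: 0.04 × 0.5 = 0.02, to 0.04 × 1.0 = 0.04. The restricted analysis flatters LY by this amount.
- The same shares reversed: −0.02 to −0.04. The restricted analysis flatters degludec.

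For scale, 0.02 to 0.04 is 5% to 10% of the 0.4 margin. The planned 90% interval has a half-width of about 1.645 × 0.135 = 0.22, so it is also 9% to 18% of that.

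**5. Whether lifting the conditions is enough.** Suppose the imputation is a regression of Week 32 HbA1c on baseline within each arm. A participant with no postbaseline data then receives, on average, the fitted value of those kept in the same arm with the same baseline. The imputed g is therefore 0, and so is the shift in step 4. If imputation is instead centred on the participant's own baseline, the imputed g in an arm is the mean fall from baseline among those kept. Taking that fall to be 0.5 to 1.0 in both arms (an assumption), the 6% and 2% shares again give 0.04 × 0.5 to 1.0 = 0.02 to 0.04. The SAP's phrase about baseline data does not settle which model is meant.

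**The case against.** The strongest reply is that little depends on this. The analysis is supplementary in the protocol and a sensitivity analysis in the SAP. Exit capture is good on paper: Visit 802 repeats the Week 32 assessments, those who stop are encouraged to continue scheduled procedures, rescued participants stay on treatment, and those who refuse follow-up are asked to an ET visit. The first injection is given at the randomisation visit, so never-dosed participants should be few. Both documents also allow a non-principal change to be justified in the clinical study report, so silence in the SAP alone is not a procedural breach. All of this stands. It limits the size of the point but does not explain why the estimand's name and its population disagree.

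Four stronger readings are tempting, and the documents support none of them:

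- *That the imputation exists for the excluded participants.* It serves anyone without a Week 32 value, including those with earlier HbA1c results.
- *That about 14 participants, or more, will be dropped.* That figure counts early leavers under an assumed timing, before exit visits.
- *That people are removed because of how they fared, and that this favours LY.* Nothing in the documents gives the reasons for a missing HbA1c or the rates by arm. The sign can go either way.
- *That deleting the condition removes the bias.* Step 5 shows that under a treatment-specific missing-at-random regression the estimate would hardly change.

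**Conclusion.** The discrepancy is real and unexplained. SAP 4.8 applies the treatment-policy label to a set selected after randomisation, whereas the protocol defines the estimand on all randomised participants. The postbaseline condition is not needed for imputation from baseline data, and it removes the participants about whom least is known from an analysis whose stated aim is to probe departures from missing at random.

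The numerical effect is probably small: zero with balanced exclusions and gaps, and 0.02 to 0.04 HbA1c points in either direction under the assumed 6% and 2% shares with a 0.5 to 1.0 point gap. Those shares and gaps are assumptions, as is even timing of dropout. The primary analysis is unaffected. The change is worth making because it costs little and lets the analysis match its name.

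**What to change.** In SAP 4.8:

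1. Define this analysis on all randomised participants, analysed as randomised (the protocol's FAS), and add the FAS to the sets in SAP 4.1.
2. Delete the conditions on dosing and on a postbaseline measurement.
3. Impute Week 32 HbA1c for everyone without it, including those with no postbaseline value.
4. State the imputation model and choose one that serves the stated aim, for example imputation centred on the participant's baseline value. Say how earlier postbaseline values are used for participants who have them.
5. Report by arm the number never dosed and the number with no postbaseline HbA1c, so the reader can judge how much rests on imputation.

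If the sponsor prefers the narrower set, it should give the reason and drop the treatment-policy label.

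The cost is SAP wording and some programming; no new data are needed. The drawback is slightly wider intervals, and possibly a slightly less favourable estimate, in this sensitivity analysis only.

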4.1. General Considerations

All data will be entered, verified, and archived at a contract research organization (CRO) external to Eli Lilly and Company (Lilly) and/or at Lilly. Data listings, summaries, and analyses will be performed by a CRO and/or by Lilly under the guidance and approval of statisticians at Lilly.

Statistical analysis of this study will be the responsibility of Lilly. Any change to the data analysis methods described in the protocol will require an amendment ONLY if it changes a principal feature of the protocol. Any other change to the data analysis methods described in the protocol, and the justification for making the change, will be described in this SAP and/or in the clinical study report (CSR). Additional exploratory analyses will be conducted, as deemed appropriate.

Unless otherwise specified, listings will be ordered by the patient ID nested within the investigator site.

The patient populations used for this study are described below:

Population and Analysis Set	Description
Entered/Enrolled Population	All study participants who sign informed consent
Randomized Population	All study participants who are randomly assigned a treatment arm
Efficacy analysis set (EAS)	Data for all randomized study participants who receive at least one dose of study medication, excluding data after using rescue medication(not acute therapy) or stopping study medication (last dose date + 10 days). In the event of a treatment error, participants will be analyzed according to the treatment they actually received.
Safety Population	All randomized study participants who receive at least one dose of study medication.
CGM Population	All randomized study participants who receive at least 1 dose of study medication, and have CGM data from at least 1 collection period.

Abbreviations: CGM = continuous glucose monitoring.

Safety analyses will be conducted using the Safety Population with all data collected during the study including treatment and follow-up period regardless of the treatment disposition status. Efficacy analyses will be conducted on the efficacy analysis set (EAS), unless otherwise specified.

Unless otherwise noted, all tests of treatment effects will be conducted at a 2-sided alpha level of 0.10 and confidence intervals (CIs) will be calculated at 90%, 2-sided. All tests of interactions between treatment groups and other factors will be conducted at a 2-sided alpha level of 0.10.

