Baseline value for a variable is defined as the last nonmissing value for this variable prior to or at randomization visit (Visit 3), unless otherwise specified.

For continuous measurements, summary statistics will include sample size, mean, median, standard deviation (SD), minimum, and maximum. For certain variables that are considered to be log-normally distributed, the geometric mean and coefficient of variation (CV) will be provided instead.

For categorical measurements, summary statistics will include sample size, frequency, and percentages. Fisher's exact test will be used. Chi-squared test will be used for multi-category variables.

A mixed-model repeated measures (MMRM) model will be used for continuous outcomes with repeated postbaseline measurements to compare treatment arms, unless otherwise noted. Treatment comparisons will be performed for the treatment difference in least-squares means (LS mean). Means and LS mean by treatment group and visit, along with the standard error of LS mean, 90% CIs of the treatment differences along with the p-value for the treatment comparison will be displayed. For the change from baseline, p-value for the within-treatment comparison will also be displayed. For selected parameters, log-transformed values will be analyzed in the MMRM model instead. The actual, change from baseline and percentage change from baseline will be presented using the derivation based on the output from the MMRM model.

In this study, all negative binomial regression will estimate Group Mean instead of LS mean and use delta method to estimate the standard error of the Group Mean (Qu and Luo 2015). Group Mean is defined as the mean response in the treatment group for the studied population. The difference between LS mean and the Group Mean is that LS mean estimates the response by taking the inverse link function on mean covariates, while the Group Mean takes the inverse link function on individual patient covariates first and then averages over all patients.

All analyses will be implemented using SAS Enterprise Guide Version 7.1 or above.

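### The HbA1c multiple imputation in SAP 4.8 is meant to probe departures from missing at random, but its one stated method is either itself a MAR method that omits interim HbA1c or a return-to-baseline scenario that is not named

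*SAP*

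**What the plan says.** SAP 4.8 (Secondary and Additional Efficacy Analyses) plans a sensitivity analysis for a treatment-policy estimand of HbA1c at Week 32.

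- **Purpose.** Missing data are multiply imputed "to assess sensitivity to departures from the missing at random assumption".
- **Method.** The next sentence gives the whole method: "the missing endpoint will be imputed multiple (for example, 100) times using the baseline data". Rubin's rules follow. No delta, tipping point, reference arm, retrieved-dropout model or return-to-baseline rule is stated.
- **Data.** "all endpoint data regardless of treatment disposition status will be included".
- **Set.** Randomised patients who took at least one dose "and have baseline and at least one postbaseline measurement".

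The primary MMRM in SAP 4.7 analyses Week 32 "together with HbA1c measure at other postbaseline visits", on the efficacy analysis set. That set drops data after rescue or from 10 days after the last dose.

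Protocol 10.3.3.2 calls the same analysis supplementary and bases it on the full analysis set, which protocol 10.2 defines from all randomised participants. It does not limit the imputation to baseline data, and it names the model that follows: "The similar MMRM model will be performed on imputed data".

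**The concern.** Two things do not fit.

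First, purpose and method. Imputing from baseline predictors assumes that, given those predictors, missing and observed outcomes follow the same distribution. That is MAR. Nothing in such a model can be varied to represent a departure.

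Second, information. The primary MMRM allows missingness to depend on earlier HbA1c. A baseline-only imputation allows it to depend on baseline alone, which is a stricter assumption. The analysis set requires a post-baseline measurement. If that means HbA1c, every imputed patient has an interim value that goes unused.

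This is the SAP's only treatment-policy analysis and its only missing-data sensitivity analysis for HbA1c. If it agrees with the primary result, that says little about robustness to MNAR. If it disagrees, the cause may simply be the discarded information. And because return to baseline is also a possible reading, two programmers could follow the sentence and run different models.

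**Working it through.** **1. The plan's own figure (protocol 10.1).** SE = 1.1 × √(1/200 + 1/100) = 0.1347. Then 0.4/0.1347 − 1.645 = 1.32, so power is 0.907 against the stated 90%. Randomised number: 300/0.80 = 375. Both reproduce and neither is in dispute. The 90% half-width is 1.645 × 0.1347 = 0.222 points, which sets the scale for what follows.

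**2. The two readings of imputing from baseline data.**

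| Reading | Type | Departure from MAR tested | Interim HbA1c used |
|---|---|---|---|
| Baseline values as predictors | MAR | none | no |
| Return to baseline | MNAR | one fixed scenario, not named | no, by design |

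**3. First reading under a true departure.** Let missing patients in one arm be worse by δ, with 20% missing per arm. The true difference is then 0.20 × δ. Large-sample simulation with 200,000 per arm, SD 1.1, and assumed correlations of −0.4 (baseline with change) and 0.75 (interim with final change):

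| δ | True difference, 0.20 × δ | Baseline-only imputation | Baseline plus interim |
|---|---|---|---|
| 0.25 | 0.05 | −0.006 | −0.007 |
| 0.50 | 0.10 | 0.003 | 0.003 |
| 1.00 | 0.20 | 0.003 | 0.003 |

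Neither imputation model sees the departure. Adding interim HbA1c therefore does not replace an explicit MNAR step.

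**4. First reading when missingness depends on interim HbA1c.** From protocol 10.1: SD of change 1.1, true difference 0, and 20% dropout as a proxy for missing Week 32 values. Assumed, because the documents do not give them: baseline SD 0.9; baseline-change correlation −0.5; Week 12 SD 1.0; Week 12/Week 32 correlation 0.7; log-odds of a missing value 0.7 per SD worse Week 12 change in one arm (odds about double), with the other arm missing completely at random at the same rate. Shift in pooled LY3209590 minus degludec, in HbA1c points, large sample:

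| Missing | Dependence in LY3209590 only | Dependence in degludec only |
|---|---|---|
| 5% | −0.017 | +0.017 |
| 10% | −0.033 | +0.034 |
| 20% | −0.064 | +0.066 |

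The sign follows from the mechanism: the poor responders go missing and are replaced from the better responders who remain, so the affected arm looks too good.

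Variations at 20% missing:
- missingness on Week 12 change beyond baseline: 0.074;
- correlation 0.5: 0.036 to 0.042; correlation 0.85: 0.087 to 0.099;
- dependence in LY3209590, half the slope (0.35) in degludec: about −0.03;
- same dependence in both arms: 0;
- different assumptions (log-odds 1.0 per HbA1c point, correlation 0.75, two equal arms): about −0.12.

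Finite-sample imputation with 250 and 125 patients (1,500 trials, 20 imputations, ANCOVA) gives −0.063 and +0.064 at 20% missing. With Week 12 added to the imputation model, the shift is within 0.001 of 0 and the mean 90% half-width falls from 0.192 to 0.186. That removal is built in, because missingness was generated from Week 12. If a later visit drives it (assumed correlations 0.75 with Week 12 and 0.9 with Week 32; LY3209590 only), baseline-only imputation shifts by −0.095, and adding Week 12 alone leaves −0.053.

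**5. Range for a delta, if one is used.** With estimate 0, equal missingness p in each arm and δ added to imputed LY3209590 values, the upper 90% limit reaches the protocol's 0.4 when δ = (0.4 − half-width)/p:
- 10%: (0.4 − 0.209)/0.10 = 1.91
- 20%: (0.4 − 0.222)/0.20 = 0.89
- 30%: (0.4 − 0.237)/0.30 = 0.54

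A simulation at 20% puts the crossing between 0.86 and 1.02, depending on the baseline correlation and the imputation model. A grid that stops at a small δ would not be informative.

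**The case against.** The strongest reply is that return to baseline is the more coherent reading. The SAP introduces its method as a specification of the stated purpose. If missing endpoints are drawn around the patient's own baseline, method and purpose agree and ignoring interim HbA1c is deliberate. This stands as a live reading. A reader might infer that the analysis is certainly a MAR model; the text does not settle that. Under return to baseline, the shifts in step 4 do not apply and the defect shrinks to an unnamed, single scenario.

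Three further replies also stand.

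- A reader might infer that no analysis model is given for the imputed data. SAP 4.1 makes an MMRM the default for repeated continuous outcomes, and the protocol names one here. Only the imputation model is under-specified.
- A reader might infer that the analysis tests nothing about MAR. It does test something: where patients are followed after rescue or after stopping treatment, which protocol 8.1.1 provides for, observed values replace what the primary MMRM handles implicitly.
- The shifts depend on how far the mechanism differs between arms and on slopes and correlations that the documents do not give. All are below the half-width of about 0.19, and true missingness may be well under 20% because off-treatment data are collected.

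The narrower population is a minor matter. SAP 4.1 lets a change be justified in the clinical study report, and site staff give the first dose (protocol 5.1.1), so few randomised patients should be undosed. No effect size is claimed for it.

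**Conclusion.** The point holds as a mismatch between stated purpose and stated method, confined to Week 32 HbA1c values that are never collected. With baseline values as predictors, the analysis contains no departure from MAR and makes a stricter assumption than the primary MMRM. With return to baseline, it is one MNAR scenario that should be named.

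Under the step 4 assumptions with dependence in one arm only, the first reading shifts the pooled difference by about 0.02 points at 5% missing and 0.04 to 0.10 at 20%. The shift is about half that when the other arm has half the dependence, and 0 when the mechanism is common to both arms. Interim HbA1c removes it only to the extent that interim values capture the mechanism.

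It might be inferred that the primary result or a non-inferiority conclusion is compromised. The documents do not support that: the primary MMRM and the sample size do not use this imputation, the SAP sets no non-inferiority rule, and the 0.4% margin appears only in protocol 10.1. This is a worthwhile correction to a sensitivity analysis.

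**What to change.** 1. **Imputation model.** State that missing Week 32 HbA1c is imputed from randomised arm, baseline HbA1c and interim HbA1c visit by visit, with off-treatment status where numbers allow. Follow it with the MMRM-type analysis that the protocol names.
2. **Explicit MNAR step.** Name at least one scenario: return to baseline, or a delta added to imputed LY3209590 values over a stated range. Report missingness by arm beside it. Carrying the delta to the point where the upper 90% limit crosses the protocol's 0.4% is an option, not a requirement; if used, the grid should reach the values in step 5.
3. **Population (minor).** Give the reason for narrowing the protocol's all-randomised set to dosed patients with a post-baseline value.

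Cost: SAP wording and a few more imputation runs. In the simulation, adding Week 12 HbA1c did not widen the interval (half-width 0.186 against 0.192), and a delta of 1.0 gave 0.195. The sensitivity interval may therefore be slightly wider under the MNAR step, and its result may be less favourable.
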